2.3. Persons Authorized to Amend the Clinical Investigation Protocol

[Redacted]

2.4. Literature Review

[Redacted]

[Redacted]

[Redacted]

[Redacted]

[Redacted]

[Redacted]

[REDACTED]

[REDACTED]

[REDACTED]

2.5. Study justification

[REDACTED] The aim of this clinical trial is to evaluate the performance, comfort, usability, and reliability of the Toffee Full Face mask in a home environment, with regards to participant views on overall experience, satisfaction, and acceptance.

[REDACTED]

2.6. Study synopsis

This will be a prospective, multi-arm, randomized, and non-blinded clinical trial, designed to evaluate the performance, comfort, and usability of the FPH Toffee Full Face mask amongst participants who have been prescribed PAP therapy by a physician.

[REDACTED]

[REDACTED]

2.7. Study Site

2.8. Clinical trial guidelines

This clinical trial will be conducted in accordance with ICH and GCP guidelines. No deviation from the protocol will be implemented without prior review and approval from the sponsor, except where it may be necessary to eliminate an immediate hazard to a participant. In such case, the deviation will be reported to the sponsor as soon as possible. Although the sponsor and the investigator are the same company, the sponsor will not be the investigator. To ensure roles are clearly defined and kept independent, there is a DOA, located within tab 3.1 of CIA-284, to clearly delineate tasks to be carried out by each of the clinical research personnel.

3. Investigator Information

4.2. Clinical Researchers

5. Clinical trial objectives

5.1. Hypothesis

[REDACTED]

5.2. Objectives

Primary objectives:

- To evaluate the Toffee Full Face mask for comfort, sealing performance, aesthetics, and usability in a home environment when used for the delivery of PAP therapy

[REDACTED]

[REDACTED]

[REDACTED]

5.3. Population

A sample of 45 participants, who currently use a full-face mask, will be recruited for the clinical trial by the investigation site.

[REDACTED]

5.4. Enrolment eligibility

Inclusion criteria:

[figure not shown]
- Persons who are ≥ 22 years of age
- Persons who weigh ≥ 66 lbs (30 kgs)
- Persons who have been prescribed PAP (APAP, BPAP or CPAP) therapy by a physician
- Persons who are compliant with PAP therapy for ≥ 4 hours per night for 70% of nights for at least two weeks prior to enrolment in the trial
- Persons who are currently using a full face mask
- Persons who have an IPAP pressure of < 30 cmH₂O
- Persons who currently use a PAP therapy device with data recording capabilities
- Persons who are fluent in spoken and written English
- Persons who possess the capacity to provide informed consent

Exclusion criteria:

- Persons who are intolerant to PAP therapy
- Persons who are required to use PAP therapy for more than 12 hours per day or for extensive periods other than sleep or naps
- Persons using nasal or nasal pillows masks
- Persons who possess, or suffer from, anatomical or physiological conditions which make PAP therapy inappropriate
- Persons who are pregnant or think they may be pregnant
- Persons who use a PAP therapy machine for the delivery of medicines, except supplemental O₂
- Persons who currently have cold or flu like symptoms at the time of recruitment
- Persons who have tested positive for COVID-19 within the previous 28 days prior to enrolment

Participants can be current users of any full-face mask.

[REDACTED]

5.5. Informed consent

Participants will be pre-screened for eligibility according to the inclusion and exclusion criteria and recruited by the three investigation sites from their database of patients by email or phone (using the RS, Appendix 15.1). If a patient is willing to participate in the clinical trial, informed consent will be obtained, individually or in groups, at the investigation site during Visit 1. A CI or the PI identified in the Delegation of Authority (DOA) will be present to witness the informed consent taking place and to answer any questions potential participants have relating to the clinical trial. Participants will be given the opportunity to read over the Informed Consent Form (ICF; Appendix 17.2), before being given an overview of clinical trial procedures and risks associated with partaking, by the CI or PI. All participants will be provided with a photocopy of the signed ICF before clinical trial procedures commence. No further physical or electronic copies of ICFs will be created. Each enrolled participant will be allocated a unique and random pre-generated 4-digit Subject Identification Number (SIN), which will be recorded in the Subject Identification Log (SIL). The SIL and all ICFs will be stored separate to all other clinical trial documentation at the investigation site to maintain anonymity of the feedback obtained from participants during the clinical trial. Details of the informed consent, such as the date and time it was obtained from participants, as well as the activities that were consented to, will also be recorded in the Case Report Form (CRF).

6. Investigational Product

6.1. Identification of the Medical Device

[figure not shown]
6.2. Pre-Clinical Testing

[figure not shown]
6.3. Device Risk Analysis and Management

6.4. Additional Precautions

6.5. Previous Clinical Experience

6.6. Essential Requirements of the Relevant Directive

Essential requirements are not applicable as this clinical trial is being conducted in New Zealand.

7. Clinical Investigation Design

7.1. Type of Investigation

This will be a multi-arm, randomized, crossover and non-blinded clinical trial. [REDACTED]

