7.2. Controls and Bias

No control group will be used in this clinical trial as it is designed to test Toffee Full Face mask for the for comfort, sealing performance, aesthetics, and usability in a home environment. [REDACTED]

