7.3. Equipment

7.4. Endpoints

Primary endpoint:

1. The Toffee Full Face mask facilitates the continued delivery of PAP therapy when used in the home

Secondary endpoints:

2. The Toffee Full Face mask, including the cushion and headgear, is comfortable when used for the delivery of PAP therapy in the home
3. The Toffee Full Face mask performs (e.g. minimal leak) adequately when used for the delivery of PAP therapy in the home
4. The Toffee Full Face mask is easy to disassemble/re-assemble when required for cleaning
5. The Toffee Full Face mask sizing guide is accurate in predicting the correct size for the participants

[REDACTED]

[REDACTED]

[REDACTED]

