9.1. Statistical Design

Next, the following data analysis strategy will be employed.

1. For each participant and requirement, it will be determined if the requirement is met by the participants' response(s) to associated questions.
2. Minitab will be used to perform a one-sided one-proportion test on each requirement using the confidence limit to confirm that the acceptance criteria has been met:

H_0 : proportion = Reliability Limit
 H_1 : proportion > Reliability Limit
Acceptance criteria:
 $P \leq 0.05$ to reject H_0

FPH as the sponsor may consult an external statistician to assist with or review the analysis of the data.

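### Does the one-sample pass/fail test merge the arms of a randomised crossover and leave the randomisation unused?

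*Combined protocol and SAP*

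**What the plan says.** The design is described in three places in the combined protocol and SAP. Section 2.6 says "This will be a prospective, multi-arm, randomized, and non-blinded clinical trial". Section 7.1 adds the crossover: "This will be a multi-arm, randomized, crossover and non-blinded clinical trial". Section 7.2 says "No control group will be used in this clinical trial". In each section the text that follows is redacted.

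The visible endpoints in section 7.4 all concern the Toffee mask alone. The primary one reads "The Toffee Full Face mask facilitates the continued delivery of PAP therapy when used in the home"; none names a contrast between arms.

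The analysis in section 9.1 begins "For each participant and requirement, it will be determined if the requirement is met", then applies a one-sided one-proportion test to each requirement against its Reliability Limit at 0.05. Section 9.2 repeats that each participant yields a pass or a fail. It gives one total, 40 completers from 45 recruited, with no number per arm or sequence. Section 9.6 defines the analysis set by fitting and home use of the mask, without reference to arm or order.

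**The concern.** In a multi-arm crossover each participant contributes at least two arm-periods. A rule that yields one outcome per participant and requirement must therefore either concern one of those periods or reduce several to one, and the visible text does not say which. If periods were combined, a requirement could be scored as met when both pass, when either passes, or on the last one worn, and the answers would differ. A weak configuration could be carried by a strong one. If the periods were instead stacked as separate rows, correlated answers from one person would be counted as independent. Randomisation also suggests a comparison, and none is planned in the visible text. Finally, section 7.1 mentions a crossover and the visible sentence in section 2.6 does not.

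**Working it through.** **The plan's own figure.** Section 9.2 gives 40 as the minimum for 80% power. It cannot be reproduced, because neither the Reliability Limits nor the assumed proportions are in the public text; the calculations by requirement are in TP-2163. It can be inverted. For n = 40 and one-sided 0.05, take the smallest r with P(X ≥ r | 40, p0) ≤ 0.05, then find the p1 with P(X ≥ r | 40, p1) = 0.80:

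| Assumed limit p0 | Pass rule | True proportion for 80% power |
|---|---|---|
| 0.50 | 26/40 | 0.70 |
| 0.60 | 30/40 | 0.79 |
| 0.70 | 34/40 | 0.88 |
| 0.80 | 37/40 | 0.94 |
| 0.85 | 38/40 | 0.96 |
| 0.90 | 40/40 | 0.99 |

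So 40 is compatible with a one-sample test on 40 outcomes. The dropout step is consistent: 40/(1 − 0.10) = 44.4, rounded up to 45. If all 40 cross over and each arm is tested on its own 40 outcomes, the power of each test is unchanged.

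**What merging would do, if it happened.** Assume two arms, n = 40 and a true pass rate p = 0.90 in each, with within-person correlation ρ. Per participant, P(both pass) = p² + ρp(1 − p) = 0.81 + 0.09ρ, and P(either passes) = 1 − (1 − p)² − ρp(1 − p) = 0.99 − 0.09ρ. Put these into P(X ≥ r | 40, ·). For the limit 0.80 (r = 37) the chance that the requirement is declared met is:

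| ρ | Both must pass | Each arm alone | Either counts |
|---|---|---|---|
| 0 | 4.0% | 42.3% | 99.9% |
| 0.5 | 14.9% | 42.3% | 82.4% |
| 0.7 | 23.5% | 42.3% | 66.6% |

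At ρ = 0.7 the both-versus-either contrast is 76% against 98% for a limit of 0.70 (r = 34), and 10% against 43% for a limit of 0.85 (r = 38). Independence is the extreme case; two wearings by the same person will usually be positively correlated.

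**Stacking.** With 80 rows and limit 0.80 the critical value is 71, and the exact type I error is 2.9%, 6.2% and 7.5% at ρ = 0, 0.5 and 0.7. But sections 9.1 and 9.2 both specify one outcome per participant, so stacked rows are not what the plan describes.

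**Does the text say that arms are merged?** Three readings fit sections 9.1 and 9.2:

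1. The test uses one Toffee arm, the other being, for example, the participant's usual mask. One row per participant is then complete and nothing is merged.
2. The test is run separately in each arm, with one row per participant in each.
3. The arms are combined into one response.

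The passages that would decide between these are not public. They include the text after the design sentences in 2.6, 7.1 and 7.2, the hypothesis (5.1), the later objectives (5.2), the timeline (7.5), the variables (7.7), the measurements (7.8) and much of the participant procedure (7.10). Section 9.3 on pass and fail criteria appears as a heading only. The visible part of 9.1 opens with a word that implies a preceding step, which is not shown.

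**Is the randomisation unused?** Randomising order of use balances order effects across configurations and needs no between-arm test to do so. With no control group and absolute endpoints, a comparison with a fixed limit answers the question posed.

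**The case for a change.** The strongest case for a change is that the decision rule itself is not redacted. The unit, the test, the sample size and the analysis set are all visible, and none mentions arm, period or sequence. In an open-label trial whose sponsor and investigator belong to the same company (section 2.8), an unstated reduction rule could be chosen after responses are seen, and stating it would take a few sentences. Masking is also real in principle: with two merged groups of 20, a limit of 0.70 and the rule 34/40, true rates of 1.00 and 0.70 pass with probability 0.61, although one group is only at the limit.

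Part of this stands. The visible text does not connect the design label to the analysis, and a reader of the public version cannot tell which arm or arms the test concerns. But silence in a heavily redacted document is not evidence that the plan is silent. The masking example presupposes the third reading, which nothing visible favours. The missing word in 2.6 is an omission in a synopsis, followed by redacted text; it does not contradict 7.1. A paired comparison of arms would serve no visible objective.

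**Conclusion.** No change follows. The mismatch between the label in 7.1 and the rule in 9.1 is a gap in what the public text shows, and the detail may well sit in the redacted passages. An analyst holding the full plan would run the stated test with one row per participant on the Toffee arm, or on each Toffee arm if there are several, and both uses agree with sections 9.1 and 9.2 as written. The claims of merged arms, unused randomisation and inflated error are not established.

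The size is conditional. Combining two arms by different rules could move the pass probability from 4% to 99.9% at correlation 0, or from 23% to 67% at 0.7, assuming two arms, 40 completers, a limit of 0.80 and 90% true success in each arm. Only the 40 comes from the documents. The conclusion would need to be revisited if the unredacted text showed that several Toffee configurations are assessed and pooled without a stated rule.

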7.2. Controls and Bias

No control group will be used in this clinical trial as it is designed to test Toffee Full Face mask for the for comfort, sealing performance, aesthetics, and usability in a home environment. [REDACTED]

7.3. Equipment

7.4. Endpoints

Primary endpoint:

1. The Toffee Full Face mask facilitates the continued delivery of PAP therapy when used in the home

Secondary endpoints:

2. The Toffee Full Face mask, including the cushion and headgear, is comfortable when used for the delivery of PAP therapy in the home
3. The Toffee Full Face mask performs (e.g. minimal leak) adequately when used for the delivery of PAP therapy in the home
4. The Toffee Full Face mask is easy to disassemble/re-assemble when required for cleaning
5. The Toffee Full Face mask sizing guide is accurate in predicting the correct size for the participants

[REDACTED]

[REDACTED]

[REDACTED]

7.5. Event timeline

[REDACTED]

7.6. Participant Compensation

[Redacted]

7.7. Variables

[Redacted]	[Redacted]	[Redacted]
[Redacted]	[Redacted]	[Redacted]
[Redacted]	[Redacted]	[Redacted]
[Redacted]	[Redacted]	[Redacted]
[Redacted]	[Redacted]	[Redacted]
[Redacted]	[Redacted]	[Redacted]
[Redacted]	[Redacted]	[Redacted]
[Redacted]	[Redacted]	[Redacted]

7.8. Measurements

[Redacted]

[REDACTED]

[REDACTED]

[REDACTED]

[figure not shown]
[REDACTED]

[REDACTED]

[figure not shown]
[REDACTED]

[REDACTED]	[REDACTED]	[REDACTED]
[REDACTED]	[REDACTED]	[REDACTED]

[REDACTED]

[figure not shown]

7.10. Participant Procedure

[figure not shown]
[REDACTED]

[REDACTED]

[Redacted]

[Redacted]	[Redacted]	[Redacted]
[Redacted]	[Redacted]	[Redacted]

Additionally, the PI may withdraw a participant at any time for the following reasons:

- Protocol violation
- Safety concerns
- Serious illness
- AE/SAE

The reason for participant discontinuation in the clinical trial is to be recorded in the CRF.

7.12. Follow-Up Plan

Participants will receive standard care from their healthcare provider throughout and after the completion of the clinical trial.

7.13. Foreseeable Complications

From the Manufacturer and User Facility Device Experience database, the common reported injuries from PAP therapy and associated interface use are pressure sores, leading to cuts, rashes, and skin abrasions and breakdown. Allergic reaction to materials in the interface can occur. Common complaints are discomfort and soreness on the areas of contact with the interface. Participants on the clinical trial are informed that they can switch back to their usual mask if required. In instances of malfunction or damage, the investigational product and its components may be replaced, as recorded in the CRF.

8. Clinical Trial Documentation

8.1. Consent and Recruitment

8.2. Case Report Form

8.4. Insurance Statement

8.5. Record of Deviations

9. Statistical Analysis

9.1. Statistical Design

Next, the following data analysis strategy will be employed.

1. For each participant and requirement, it will be determined if the requirement is met by the participants' response(s) to associated questions.
2. Minitab will be used to perform a one-sided one-proportion test on each requirement using the confidence limit to confirm that the acceptance criteria has been met:

H_0 : proportion = Reliability Limit
 H_1 : proportion > Reliability Limit
Acceptance criteria:
 $P \leq 0.05$ to reject H_0

FPH as the sponsor may consult an external statistician to assist with or review the analysis of the data.

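### As written, section 9.1 lets participants' answers alone decide pass or fail, apparently including the primary endpoint of continued PAP delivery, although every participant must use a data-recording PAP device

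*Combined protocol and SAP*

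**What the plan says.** All references are to the combined protocol and SAP.

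- **Scoring (9.1, rule 1).** "For each participant and requirement, it will be determined if the requirement is met by the participants' response(s) to associated questions". Rule 2 then tests each requirement with a one-sided one-proportion test at 0.05 against a Reliability Limit whose value is not visible.
- **Primary endpoint (7.4).** "The Toffee Full Face mask facilitates the continued delivery of PAP therapy when used in the home". No metric or threshold is visible.
- **Endpoint 3 (7.4).** "The Toffee Full Face mask performs (e.g. minimal leak) adequately when used for the delivery of PAP therapy in the home". Again no visible metric.
- **Devices and entry standard (5.4).** Inclusion requires "Persons who currently use a PAP therapy device with data recording capabilities" and also "Persons who are compliant with PAP therapy for ≥ 4 hours per night for 70% of nights for at least two weeks prior to enrolment".
- **Design (7.1, 7.2).** "This will be a multi-arm, randomized, crossover and non-blinded clinical trial", but also "No control group will be used in this clinical trial". These two statements need reconciling in their own right.
- **Usual mask (7.13, 9.6).** "Participants on the clinical trial are informed that they can switch back to their usual mask if required". Section 9.6 gives firm proof that another mask was worn as an example of a reason to leave a participant out of the analysis, with the reason documented.
- **Sample size (9.2).** At least 40 participants, with 45 recruited. The assumed proportions come from an earlier trial (TR-32203) or earlier validation trials, and the calculations are in TP-2163.

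**The concern.** Comfort and ease of re-assembly are matters of judgement, and a questionnaire suits them. Whether PAP was delivered is a quantity that a recording device can supply. Under rule 1, a participant with short recorded use who answers favourably is a pass.

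The option to return to the usual mask adds a second problem. Someone who spent some nights on the usual mask can truthfully say that therapy continued, although the study mask did not deliver it on those nights. If the switch is proven, section 9.6 may instead remove that participant, so a possible failure of the primary endpoint leaves the denominator.

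Participants know which mask they wear, and sponsor and investigator belong to the same company. Section 2.8 separates those roles through a delegation log, which helps with conduct but does not make participants' answers blind. At stake is a statement that the mask sustains therapy which the participants' own device records might not support.

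**Working it through.** **1. The plan's own figure.** N = 40 cannot be reproduced, because the Reliability Limits and assumed proportions are not in the visible text. The 45 is consistent with the dropout allowance: 5/45 = 11.1%, and 40/(1 − 0.10) = 44.4, rounded up to 45. Nothing below depends on whether 40 is right.

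**2. The passages side by side.** Rule 1 has no exception by endpoint. Two cases are possible:

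- Hidden sections score endpoint 1 from recorded use. Rule 1 then contradicts them and needs correcting.
- Hidden sections do not. Rule 1 then applies as it reads, and answers decide the primary endpoint.

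In both cases 9.1 needs a sentence naming the source that decides endpoint 1.

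**3. Effect of favourable answers (illustration).** From the plan: n = 40, one-sided alpha 0.05. Assumed: the limit p0, an exact binomial test, a true success rate exactly at p0, and a share f of true failures answering as if the requirement were met.

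- Pass mark r: the smallest r with P(X ≥ r | 40, p0) ≤ 0.05. For p0 = 0.80, P(X ≥ 36) = 0.076 and P(X ≥ 37) = 0.028, so r = 37.
- Apparent rate: q = p0 + (1 − p0) × f. For p0 = 0.80 and f = 0.5, q = 0.80 + 0.20 × 0.5 = 0.90.
- Probability of passing: P(X ≥ r | 40, q). For q = 0.90, P(X ≥ 37) = 0.423.

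| Assumed limit | Pass mark | f = 0 | f = 0.2 | f = 0.5 |
|---|---|---|---|---|
| 0.70 | 34/40 | 2.4% | 12.3% | 60.7% |
| 0.80 | 37/40 | 2.8% | 9.8% | 42.3% |
| 0.90 | 40/40 | 1.5% | 3.6% | 12.9% |

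**4. Errors in the other direction.** If 5% of true successes also answer that the requirement was not met, then q = 0.95 × p0 + (1 − p0) × f. For p0 = 0.80 and f = 0.2, q = 0.76 + 0.04 = 0.80, and the probability returns to 2.8%. At f = 0.5, q = 0.76 + 0.10 = 0.86, and it is 17.0%.

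**5. Effect of the denominator (illustration).** Suppose all 45 are fitted and use the mask, 5 switch back and are excluded under 9.6, and 37 of the other 40 pass. At an assumed 80% limit, 37/40 = 92.5% gives p = 0.028, a pass. With the 5 counted as not met, 37/45 = 82.2% and P(X ≥ 37 | 45, 0.80) = 0.44, a clear fail; 41 of 45 would be needed (P = 0.038, against 0.090 for 40). The number of switch-backs is assumed.

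**The case against.** The strongest reply is redaction. Variables (7.7), Measurements (7.8), most of the participant procedure (7.10) and the text after the endpoints are blacked out, and Pass and Fail Criteria (9.3) shows only a heading. Section 9.1 opens mid-sequence, so an earlier step is not visible. The device criterion in 5.4, and references on adherence tracking and leak profiles, suggest that device data may be planned. Nor does any visible text map endpoint 1 to a named validation requirement. All of this stands.

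A reader might therefore go too far in three ways:

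- **That endpoints 1 and 3 measure opinion rather than therapy, or that device data are not collected.** The documents do not support stating this as fact, since the sections that would settle it cannot be seen.
- **That 5.4 defines delivery.** Its 4-hour, 70% standard describes compliance before entry only.
- **That recorded leak should decide endpoint 3.** No leak threshold appears in the documents, and leak metrics may differ between device makes. A change of the deciding measure is debatable there.

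Two further points have weight. Section 2.5 puts participants' views within the trial's aim, so questionnaires belong in it. And the bias figures rest on assumed limits and misreporting rates; step 4 shows that modest errors in the other direction can cancel the effect.

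Redaction does not answer the point about rule 1 itself. That sentence is visible and current, and it would have to change even if the hidden sections specify device data. Section 9.6 does not close the usual-mask gap either: it requires firm proof, and it excludes the participant where a failure might be counted.

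**Conclusion.** The point holds as a fault in the visible scoring rule. Rule 1 decides every requirement, apparently including the primary endpoint, from answers in a non-blinded trial, when a less biased source is available on devices that participants must already use. It does not establish that the endpoints measure only opinion, or that this trial's result will be biased.

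The size cannot be fixed from the documents. At an assumed 80% limit, the chance of a false pass rises from 2.8% to 42% if the apparent rate becomes 90%; across the limits and non-zero misreporting shares in the table it runs from 3.6% to 60.7%, and lower with reverse errors. These figures show how the rule could behave and are not estimates for this trial. The change should be made for endpoint 1. For endpoint 3, recorded leak should be supportive only.

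**What to change.** 1. **Endpoint 1.** Amend 9.1 rule 1 so that pass or fail comes from device-recorded use on nights with the study mask, against a threshold set in advance. The plan's own entry standard (at least 4 hours on 70% of nights) is a candidate, for the sponsor to justify. If hidden sections already do this, align rule 1 with them.
2. **Usual-mask nights.** State how they count, and reconcile this with 7.13 and 9.6 so that switching back does not simply remove a participant from the denominator.
3. **Endpoint 3.** Report device-recorded leak as supportive objective data, described by device make.
4. **Questionnaires.** Keep them as the deciding source for comfort and ease of re-assembly.
5. **Sample size.** Recheck the assumed proportion behind n = 40 for endpoint 1, since the proportion taken from earlier trials may not apply to a device-based criterion.

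The cost is wording in 9.1 and 9.6, a download from devices that eligibility already presupposes, and a rule for differing makes. The sponsor must also confirm that the sleep diary records which mask was worn each night, which its visible title does not show. The pass rate may be less favourable than under questionnaire scoring.
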